128 **Primary objective:** The aim of the proposed study is to determine whether 10 days of
129 post-acute inpatient rehabilitation followed by a home programme is superior to a home
130 programme alone.

131 **Study design:** Two arm, parallel randomised controlled trial with third observational
132 group.

133 **Planned sample size:** A minimum of 140 participants, minimum of 70 in each arm.

134 **Selection criteria:** Patients presenting to Fairfield or Sutherland Hospital for a primary
135 total knee replacement, and who can comprehend the protocol, and who are not
136 predisposed (due to lack of social supports or multiple physical impairments) to be
137 discharged to an inpatient facility.

138 **Study procedure:** Patients will be screened, consented and thus enrolled pre-operatively.
139 Day 1 after surgery they will be randomized to 1 of the 2 treatment arms – inpatient
140 rehabilitation at Braeside or Sutherland Hospital (10 days) or to usual care, a monitored
141 home programme, provided by Fairfield, Sutherland or Campbelltown Hospitals.

142 **Statistical considerations:** *Sample size calculation:* The primary endpoint in this trial is
143 function at 6 months post-surgery, measured using the outcome of a Six-Minute Walk Test
144 (6MWT). A total minimum of 140 patients (minimum of 70 patients in each group) will
145 provide 80% power and 95% confidence to detect a difference of 60m (SD 100m) in the
146 in-hospital rehab group at 6 months when compared to the home based programme, and
147 allows for 10% loss to follow-up.

148 **Duration of the Study:** 3.5 years

149

150

151

152		TABLE OF CONTENTS
153		
154	BACKGROUND	
155	Disease Background	
156	Rationale for Performing the Study	
157		
158	STUDY OBJECTIVES	
159	Primary Objective	
160	Secondary objectives	
161		
162	STUDY DESIGN	
163	Design	
164	Study Groups	
165	Number of Participants	
166	Number of Centres	
167	Duration	
168		
169	PARTICIPANT SELECTION	
170	Inclusion Criteria	
171	Exclusion Criteria	
172		
173	STUDY OUTLINE	
174	Study Flow Chart	
175	Investigation Plan	
176	Recruitment and Screening	
177	Informed Consent Process	
178	Enrolment Procedure	
179	Randomisation Procedure	
180	Study Procedures	
181		
182	SAFETY	
183	Adverse Event Reporting	
184	Serious Adverse Event Reporting	
185	Data Safety and Monitoring Board - membership and responsibilities	
186	References to national and international guidelines on research in humans	
187	Early Study Termination	
188		

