287 necessary after TKR for patients with osteoarthritis (OA) who could otherwise be discharged
288 directly home.

289 The main hypothesis to be tested by the proposed study is that TKR recipients who receive
290 inpatient rehabilitation in addition to participating in a home programme, compared to
291 patients who participate in a home programme only, will achieve a superior level of mobility
292 at 6 months post surgery. If superiority is shown, a cost-effectiveness analysis will be
293 undertaken.

294

295 Primary outcome

296 The primary outcome variable is walking distance at 6 months post surgery, measured using
297 the Six-Minute Walk Test (6MWT)^{17, 19}. Function measured by this test is a composite of
298 several factors targeted in rehabilitation programmes after TKA such as lower limb strength,
299 knee range of motion, and balance^{17, 18, 19, 20, 21}. The test is highly reproducible within the
300 individual²², is likely to be less susceptible to misinterpretation and less culturally sensitive

301 than patient-reported outcomes, and does not appear to suffer from the floor or ceiling effects
302 associated with many patient-reported outcomes²³ Together, these attributes mean the results
303 for our primary outcome should be readily translatable to any TKA cohort. Finally, a
304 functional outcome based on a physical test is a novel choice as a primary outcome in this
305 field with most TKA rehabilitation studies focusing on patient-reported outcomes^{12, 17, 18, 20, 24}.

306

307 2.2. SECONDARY OBJECTIVE

308 Secondary hypotheses to be tested relate to patient-reported knee pain and function, health-
309 related quality of life, and knee joint mobility. Superiority in these outcomes will be evident
310 at six months after surgery.

311

312 3. STUDY DESIGN*

313 3.1. DESIGN*

314 Two-arm, parallel randomised controlled trial with third observational group.

315 3.2. STUDY GROUPS

316 Two study groups (treatment arms).

317 1) HI – Hospital inpatient rehabilitation group

318 2) HO – Home-based rehabilitation group

319

320 Description of the interventions

321 (HI): Those allocated to the HI will be admitted to Braeside or Sutherland Hospital's
322 Rehabilitation Unit for 10 days. Informed by the private sector,²⁵ HI patients will receive
323 twice-daily supervised physiotherapy. Supervised therapy will comprise 1-1.5 hr of class-
324 based exercises and 1-1.5 hr of 1-to-1 therapy. After discharge, patients will be provided with

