518 An independent DSMB will be established to monitor the trial safety and where appropriate
519 provide advice on issues regarding the scientific aspects of study conduct (eligibility,
520 recruitment rates, and compliance/cross-overs) study safety (serious adverse events) and any
521 emerging evidence as it relates to the trial. This board will comprise at least a rehabilitation
522 physician, physiotherapist and a statistician/epidemiologist.

523 **Early Termination**

524 The study will be terminated early if access block to Braeside hospital becomes
525 unmanageable because of the study. The primary investigator will inform the HREC if the
526 study is terminated early. All enrolled patients will be notified of study termination by the
527 primary investigator and future follow-ups will only be completed if the patient wishes.

528

529 **7. BLINDING AND UNBLINDING**

530 Any investigator or research officer involved in the follow-up assessments will be blinded to
531 the treatment allocation. Patients and carers will be asked not to disclose their treatment
532 allocation at the follow-up assessments. Blinding will not be possible for the treating
533 physiotherapists, or the participants.

534

535 **8.STATISTICAL CONSIDERATIONS**

536 The primary endpoint in this trial is function at 6 months post surgery, measured using the
537 outcome of a Six-Minute Walk Test (6MWT). A total minimum of 140 patients (minimum of
538 70 patients in each group) will provide 80% power and 95% confidence to detect a difference
539 of 60m (SD 120m) in the in-hospital rehab group at 6 months when compared to the home
540 based programme, and allows for 10% loss to follow-up.

541

542 **9. CONFIDENTIALITY AND STORAGE AND ARCHIVING OF STUDY** 543 **DOCUMENTS***

544 As per 2.2.2 in the Australian Code for the Responsible Conduct of Research,²⁷ the study data
545 will be stored in the researcher's own department. That is, in the office of [name] at
546 Braeside Hospital. The paper data will be stored in a locked cabinet in office which is locked
547 when no research personnel are present and the database will be stored on [name] M
548 drive and be password protected. As per 2.2.3,²⁷ the researchers and the physiotherapists
549 involved in providing therapy for the patients at Braeside, Sutherland, Campbelltown and
550 Fairfield Hospitals have agreed that: the researchers will store study assessment data (such as

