697 the participants' study allocation.

698 The primary endpoint in this trial is functional mobility at 6 months post-surgery measured
699 using the distance walked during a 6MWT. Seventy participants in each group (140 in total)
700 will provide 80% power at a significance level of 5%, to detect an increase in walking
701 capacity from 400 m to 460 m between the Home and Inpatient groups respectively in the
702 six-minute walk test at six months post-surgery, assuming a SD of 120 m and a drop-out rate
703 of $< 10\%$. With the addition of a second recruitment site, the definitive sample is expected to
704 be approximately 160 participants, allowing us to increase the power of the study.

705 In the absence of data describing the minimum clinically important difference (MCID) for the
706 6MWT, a sub-study is now included to evaluate the MCID/MID for measured mobility in
707 this population.

708 **Descriptive analyses at baseline**

709 Comparability of intervention groups will be investigated at baseline. Descriptive statistics
710 will be presented, including summary statistics of potential confounding variables.

711 **Analyses subsets**

712 Data analysis will be completed using the principle of intention-to-treat (ITT) [1]. We will
713 include all randomised participants regardless of level of compliance with the protocol. The
714 primary outcome variable is distance measured using the outcome of a 6MWT at 26 weeks.

715 Analysis of covariance will be used for this primary outcome, with treatment group as the
716 main study factor and walking distance at baseline, weight, co-morbidities and patient
717 preference as covariates. For participants with a missing outcome measure at 26 weeks, an
718 imputation method will be used [1,2].

719 The secondary outcome variables include the 6MWT at 10 and 52 weeks post-surgery, the 15
720 metre walk test, EQ5D, Oxford Knee Score, KOOS and knee ROM at most post-surgery time
721 points.

722 Mixed model analyses will be used for the continuous variables measured repeatedly at 10,
723 26 and 52 weeks to estimate the treatment group by time effects. These analyses incorporate
724 the missing data that may occur at the follow up occasions. Baseline measurements of the
725 outcome variables, together with factors, such as weight, co-morbidities and patient
726 preference, will be included as covariates. For the binary outcome measured 10, 26 and 52

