727 weeks (knee flexion $> 100^\circ$ or $\leq 100^\circ$), a Generalised Estimating Equation model will be
728 used to test the treatment effect, with the adjustment of the covariates as above.

729 For the sensitivity analysis, we will also perform a per protocol analysis including only
730 patients who complied with the treatment protocol. Compliance for HI group will be defined
731 as attendance of a minimum of 7 days of inpatient rehabilitation, along with attendance at no
732 less than two outpatient sessions and no more than five. Compliance for the HO group will be
733 defined as attendance at no less than two outpatient sessions and no more than five.

734 There will be procedures put in place to minimise loss to follow-up, such as obtaining
735 multiple contact details at time of consent and reminders that assessments are due. The age,
736 gender and height of participants will be used as stratification variables in the randomisation
737 procedure via a minimisation algorithm. The mixed model analysis indicated above will
738 include these three variables as additional covariates to incorporate the possible within
739 treatment group correlation associated with by stratification [3].

740 For the analyses involving the observational arm, the change score in the primary outcome
741 will be compared between the observational group and those in the randomised home group
742 adjusting for other covariates. A lack of significant difference in scores between the two
743 groups will suggest there is no strong preference effect in this trial and we may not need to
744 include preference as a covariate in the RCT analyses. To be consistent with the two RCT
745 groups, we will aim for a minimum 64 participants in the observational group.

746 Cost-effectiveness analysis will be undertaken if the inpatient arm is shown to be superior.
747 Due to limited funding, we will no longer utilize data from the PBS or Medicare. Costs will
748 be based on standardized unit prices and based on patient diaries of expenses.

749

750

751 **References**

- 752 1. Sterne J, White I, Carlin J et al: Multiple imputation for missing data in epidemiological
753 and clinical research: potential and pitfalls. *BMJ* 2009; 338: b2393.
- 754 2. Donders R, van der Heijden G, Stijnen T, Moons K: Review: A gentle introduction to
755 imputation of missing values. *J Clin Epi* 2006 59: 1087e-1091.

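### Read literally, the SAP's per-protocol rule keeps home-arm patients who had inpatient rehabilitation, provided they attended two to five outpatient sessions

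*Supplement*

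**What the plan says.** The passage at issue is in the SAP under Analyses subsets. The primary analysis is by intention to treat and will "include all randomised participants regardless of level of compliance with the protocol. The" primary outcome is the six-minute walk distance at 26 weeks. The SAP then adds a second analysis set: "For the sensitivity analysis, we will also perform a per protocol analysis including only" those who complied with the treatment protocol. Compliance is defined arm by arm:

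- HI: "as attendance of a minimum of 7 days of inpatient rehabilitation, along with attendance at no" fewer than two and no more than five outpatient sessions.
- HO: "defined as attendance at no less than two outpatient sessions and no more than five".

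The comparator is described consistently elsewhere. The primary objective in the protocol Summary asks whether "post-acute inpatient rehabilitation followed by a home programme is superior to a home" programme alone. Section 2.1 sets the inpatient arm against "patients who participate in a home programme only, will achieve a superior level of mobility". The SAP Background describes the control as the hybrid home programme by itself.

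Cross-overs are mentioned once, in protocol section 6.2, among the subjects on which the monitoring board may advise: "recruitment rates, and compliance/cross-overs) study safety (serious adverse events) and any" emerging evidence. Neither the protocol nor the SAP says how a patient who crosses over is to be classified.

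**The concern.** Inpatient rehabilitation is the one element that separates the two arms, and the HO compliance rule is silent on it. A per-protocol set is meant to hold patients who received the treatment they were allocated. As worded, this one drops HI patients with too little inpatient exposure but does not drop HO patients who had inpatient exposure.

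This matters because the per-protocol analysis is the only planned analysis that could remove cross-overs; intention to treat rightly keeps everyone as randomised. If the primary comparison shows no difference, readers will ask whether home-arm patients also received inpatient care. The literal rule weakens the answer. It also leaves room to decide, after the data have been seen, whether such patients belong in the set.

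The point concerns the missing exposure condition only. It does not question the limits on outpatient sessions.

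**Working it through.** **1. The two rules side by side (SAP, Analyses subsets)**

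| Condition | HI | HO |
|---|---|---|
| Outpatient sessions | 2 to 5 | 2 to 5 |
| Inpatient rehabilitation | at least 7 days | none stated |

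The HO rule is the HI rule with the inpatient condition removed, so any course of care that satisfies the HI rule also satisfies the HO rule. An HO patient with 10 inpatient days and two sessions meets both. A cross-over with fewer than two or more than five sessions is already excluded.

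**2. Can the situation arise?** Protocol section 5.6 places randomisation in the days after surgery, before discharge from acute care. (It says 3-4 days; the Summary says Day 1. These should be reconciled, but on either the discharge destination can still change after allocation.) Section 4.2 excludes patients likely to need inpatient discharge, and section 5.6 removes anyone found to need rehabilitation before allocation. Nothing covers a need that arises after allocation. The route is narrowed, not closed.

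**3. The plan's own figure.** Inputs from the SAP under Outcome measures: difference 60 m (400 vs 460 m), SD 120 m, 5% level (taken as two-sided), 80% power, drop-out 10%.

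n per arm = 2 × (1.960 + 0.842)² × (120/60)² = 62.8, rounded up to 63. Allowing for drop-out, 63 / 0.90 = 70, which matches the stated 70 per group.

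**4. Size under dilution.** Let c be the share of the retained HO set that had inpatient rehabilitation. The documents give no value, so c is an assumption. If these patients gain the full planned effect, the HO mean rises by 60c and the contrast is 60 − 60c = 60(1 − c). The standard error with 63 per arm is 120 × √(2/63) ≈ 21.4 m. Power is for a two-sided 5% normal test.

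| c | Contrast, kept | Shift | Shift / SE | Power, kept | Power, removed |
|---|---|---|---|---|---|
| 0 | 60 m | 0 | 0 | 80.1% | 80.1% |
| 5% | 57 m | 3 m | 0.14 | 76.0% | 79.1% |
| 10% | 54 m | 6 m | 0.28 | 71.4% | 78.0% |
| 20% | 48 m | 12 m | 0.56 | 61.2% | 75.4% |

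The last column keeps the 60 m difference, reduces the HO arm to 63(1 − c) and assumes that removal causes no selection. The power figures serve for comparison only: the real per-protocol arms will not number exactly 63.

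**5. The opposite case.** Suppose the cross-overs are patients recovering poorly who walk 100 m less than other HO patients (an assumption with no source in the documents). At c = 10% the HO mean falls by 0.10 × 100 = 10 m, and keeping them widens the contrast by 10 m in favour of HI. The direction of the error therefore depends on who crosses over and cannot be fixed in advance.

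**The case against.** The strongest reply is that the sentence introducing the set already settles the matter. It admits only "patients who complied with the treatment protocol. Compliance for HI group will be defined" by arm. The treatment protocol for HO is a home programme and nothing more, so an HO patient admitted for inpatient rehabilitation has not complied, and the session counts merely set the dose. This is a fair reading and probably the intended one. But the definitions that follow are what an analyst will program, and they do not contain it. The gap in the wording stands.

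Several further objections limit the point and should be accepted:

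- A reader might infer that the protocol expects cross-overs. It does not say so. Section 6.2 only lists them as a topic for the monitoring board, with no rate or direction. The one description of unplanned transfer to inpatient rehabilitation (section 3.2) concerns patients who declined the trial.
- Sections 4.2 and 5.6 screen against this route, and the home programme is standard care at these hospitals, so a low rate is plausible.
- A reader might infer that the analysis could say nothing about a null primary result. That goes too far. It still removes HI patients with under 7 inpatient days, and even at c = 20% it retains 48 of the 60 m.
- Excluding cross-overs has its own bias. If they crossed over because of poor recovery, the remaining HO set is healthier than the HI set, which leans against HI.

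**Conclusion.** The point holds as a defect in a stated operational rule. Taken literally, the HO per-protocol definition admits patients who received the inpatient package, which conflicts with the comparator given in the protocol Summary, section 2.1 and the SAP Background.

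Its size is unknown. With full benefit in the cross-overs, each 5% of the retained HO set takes 3 m off an expected 60 m. A few percent is small against a standard error of about 21 m; 20% would matter. The rates, the full-benefit assumption and the 100 m deficit are illustrations, not figures from the plan. It would be wrong to claim a known direction, since dilution and selective cross-over pull opposite ways.

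Nor should a reader infer that the trial's main conclusion is at risk. Intention to treat is primary and keeps all patients as randomised, so only the sensitivity analysis is affected. The repair is worth making because it is cheap and removes a choice that would otherwise be open after unblinding.

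**What to change.** In the SAP, under Analyses subsets, add to the HO per-protocol definition that the patient received no inpatient rehabilitation after randomisation, alongside the existing session condition. Name the source: therapist proformas, patient diaries or hospital records. Section 3.2 of the protocol has proformas recording therapy provided and diaries recording healthcare use, so the information should be recoverable. Discharge destination is not a named data item, so this should be confirmed before the definition is locked.

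Report the number of cross-overs in each direction beside the intention-to-treat and per-protocol results. Intention to treat stays primary.

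The cost is one clause and two counts. The HO per-protocol set becomes slightly smaller: if 10% are removed from 63, about 57 remain, and power goes from 80.1% to 78.0% under the assumptions above. Selection is possible if patients crossed over because they were recovering poorly, and the report should say so when interpreting the per-protocol estimate.
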